2.4 RANDOMIZATION

Following a determination of eligibility, subjects will be randomly assigned to one of two treatment arms (1:1 ratio), after stratification on the basis of gender, disease severity (DLCO <35% of predicted values), and current use of either/both pirfenidone and/or nintedanib. These stratifications will ensure ~equal proportions of severely ill patients, and ~equal proportions of males, in each arm. Male IPF patients have worse prognoses than females (1-4). Randomization assignments will be made in random block sizes of 2 and 4.

Randomizations will occur on the day of initial treatment, to reduce the possibility of "wasting" a randomization on a patient who fails to return for treatment.

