- **e.) Hospitalizations** Indirect evidence of treatment efficacy could also be discerned by reductions of subsequent needs for hospital admissions. The frequencies and durations of hospitalizations among trial subjects will be tabulated and analyzed.
- **f.) AE Monitoring-** The National Cancer Institute Common Toxicity Criteria Scale will be used to define grades (severity) of AE and toxicities. An AE is defined as any untoward medical occurrence in a subject, regardless of its relationship to these treatments. Toxicity is an AE with a direct relationship to the study drug. All toxicities are AE, but not all AE are toxicities.

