2.9 DATA AND POWER ANALYSES

2.9.1 Power Analyses:

Given the initial nature of this trial, definitive power calculations are speculative. Nonetheless, even moderate efficacy of the experimental treatment (as we anticipate) will produce evidence of same. Assuming a type 1 error rate of 0.05, a two-sided alternative hypothesis, n = 29/arm, and very conservative event rates (i.e., reduction of autoantibody titers in 33% of the experimental arm subjects, and 3% reduction in placebo controls) there is 80% power to detect a statistically significant effect.

The sample size of 58 for this clinical trial is based on exposing a minimum number of patients to potential risks of the experimental treatment, while still obtaining useful information. Analyses will follow intention to treat principles. Missing data techniques (e.g., multiple imputation) will be employed for subjects lost to follow-up, had transplants, or those who died. A sensitivity analysis will also be conducted in which transplantations and deaths will be considered failures.

2.9.2 Data Analyses:

Data analyses begin by describing baseline demographic and medical characteristics of the cohorts. Descriptive statistics, including measures of central tendency and dispersion, will be computed for continuous data (e.g., age). Frequency distributions will be estimated for categorical data (e.g., gender). To ensure balanced random assignments, treatments are examined in relationship to demographic and medical characteristics using the appropriate parametric (e.g., t-test) or nonparametric test (e.g., chi-square, Wilcoxon tests). Reduction of autoantibody titers from baseline to the nine-month follow-up visit will be calculated as a binary indicator (yes/no). A Fisher's Exact test will be used to compare rates of autoantibody titer reductions between the two groups. To control for the stratification variables, an exact logistic regression model will be used, including main effect for treatment and the stratification variables. Unbalanced baseline characteristics will also be included in the regression model.

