Linear regression models will be used to assess the treatment effect on continuous variable secondary endpoints. Main effects will include treatment, the stratification variables, and unbalanced baseline characteristics. Both the proportion of individuals with AEs and the count of AEs per person will be compared by treatment. A logistic regression model will be used to compare the proportion of subjects with acute exacerbations, hospitalizations, or adverse events (AEs) by treatment group, with main effects as described above. A negative binomial model will be used to evaluate the average count of AEs per subject by treatment group. For all models, the model assumptions (e.g., normality of residuals, over dispersion) will be investigated. If the assumptions are violated, transformations will be investigated. If adequate transformations cannot be identified, nonparametric approaches will be utilized. Small cell sizes may exist and exact methods may need to be employed.

Additional exploratory analyses will be conducted. This may include the use of mixed-effects regression models to examine the longitudinal course of the outcomes as well as survival analyses (e.g., Kaplan-Meier curves, log-rank test, Cox proportional hazards models) to evaluate time to event outcomes, such as time to death.

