Admittedly, expectation of treatment effects on forced vital capacities (or frequencies of acute exacerbations) is much more speculative than the anti-HSP70 IgG measures. We nonetheless anticipate reductions of autoantibodies in the experimental arm, especially if persistent (e.g., for ≥6 months) could possibly result in better preservation of lung function, even in this small cohort. IPF tends to rapidly progress compared to many other chronic lung diseases, so even a relatively minor alteration of the natural history might be detectable (we admit to some high risk:high yield speculation here- but note too Figure 3). We will also record and collate other clinical parameters (notably patient survival), but these are not formal end-points of this more exploratory, early-phase clinical trial. Based on multiple other rituximab studies involving thousands of patients with various autoimmune diseases (29-39), we do not believe high grade AE will be significantly more frequent among experimental trial subjects compared to placebo.

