APPENDIX A. STUDY ASSESSMENT TABLE AND EVENTS

Visit Number	Pre-Treatment		Treatment				Post Treatment Follow-Up								
	1	2	3	4	5 ^β	6	7#	8	9 [‡]	10	11	12 [‡]	13	14	15 [‡]
Day (D) or Month (M) from First Treatment	Screen*	Base Line*	D 1	D2	D 14	D 15	M 1	M 2	M 3	M 4	M 5	M 6	M 7	M 8	M 9
Informed Consent	x														
Inclusion Exclusion Criteria	×														
History and Medication Review	x		x		×		х		x			x			×
Physical Exam	x		х		х		х		х			х			x
Screening Lab Tests: ANA,RF, anti-Ro, Anti-La, anti-RNP, anti-Jo-1, HCV, HBsAg, HBcAb, HIV Ab, serum pregnancy test	x														
Complement (C3,C4)		×					×		х.			×			x
CBC/Diff/plat		x			_		x		х			×			×
Chest CT scan		×													×
Spirometry, DLCO, Exercise SaO2, 6 min walk, Borg		x					x		x			x			x
Experimental Immunology		x					x		x			х			х
Randomization (1:1)			х												
Study Treatment			х		x										
AE Assessment	х	х	x	х	x	х	х	х	x	х	х	х	х	x	х
Phone assessment				×		х		х		х	x		х	x	
Study Completion															x

^{*}Screening and Baseline evaluations can occur concurrently, or on separate days, as long as all tests and procedures are performed in the 14 days prior to first study treatment. Chest CT can be performed within the 30 day interval prior to first study

[#] The Months 3, 6 and 9 have a +/- seven day window.

The Month 1 visit has a +/- five day window.

The Months 3, 6 and 9 have a +/- seven day window.

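### The planned adverse event comparisons pool all grades with no onset window, so Section 2.9.2 has no analysis of the protocol's own expectation about high-grade events

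*Combined protocol and SAP*

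**What the plan says.** AE rates are a formal secondary endpoint (Section 2.8.2, item f), and the second aim in Section 1.2 expects an acceptable AE profile. Five places bear on how they are analysed.

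- **Analysis.** Section 2.9.2 states: "Both the proportion of individuals with AEs and the count of AEs per person will be compared by treatment". The proportion goes into a logistic model and the count into a negative binomial model. No grade, seriousness, relatedness or time window is named.
- **Expectation.** Section 2.10.2 says: "we do not believe high grade AE will be significantly more frequent among experimental trial subjects compared to placebo".
- **Definition.** Section 2.8.2 says: "An AE is defined as any untoward medical occurrence in a subject, regardless of its relationship to these treatments". Section 5.4.4 is narrower and refers to participants who received study drug.
- **Grading.** Sections 2.2, 2.8.2 and 5.4.4 provide for NCI toxicity grades; Section 5.4.4 describes grades 1 to 5.
- **Collection.** The "AE Assessment" row in Appendix A is marked at every visit, including Screen and Base Line.

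**The concern.** The protocol frames its safety expectation by severity and collects severity, but the analysis section does not use it. Under the Section 2.8.2 definition, breathlessness, cough and other consequences of IPF count as AEs. The disease is described as progressive (Sections 1.3 and 2.8.2), and subjects are contacted about monthly for nine months.

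Pooling all grades can mislead in two directions. Background disease events can swamp a modest excess of severe events. Conversely, Section 5.1.2 lists fever, chills, headache and nausea as common with rituximab, so mild infusion symptoms could produce an all-grade difference that says nothing about severe harm. The trial is meant to inform the design of a Phase III study, and its all-grade results would not say whether severe events differ between the arms.

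**Working it through.** **Inputs from the documents.** Section 2.9.1: "Assuming a type 1 error rate of 0.05, a two-sided alternative hypothesis, n = 29/arm". The same paragraph assumes "reduction of autoantibody titers in 33% of the experimental arm subjects, and 3% reduction in placebo controls" and concludes that "there is 80% power to detect a statistically significant effect". No power figure is given for AEs. The only AE rates are for single terms in rheumatoid arthritis (Section 3.4: 6% to 8% on rituximab, 4% to 6% on placebo). Every AE rate below is therefore an assumption.

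**Step 1: reproduce the plan's figure.** Exact power of the two-sided Fisher test is the sum, over all pairs (x, y) with p ≤ 0.05, of Bin(x; 29, p1) × Bin(y; 29, p2). With 0.33 and 0.03 it is 0.810, which matches the stated 80%. The same enumeration is used next as an unadjusted stand-in for the planned logistic model.

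**Step 2: any AE, yes or no.** Take the extreme case in which all 29 rituximab subjects have an AE. Then p ≤ 0.05 requires 23 of 29 (79%) or fewer on placebo (29/29 versus 23/29 gives p = 0.023). Power is the probability of that placebo result:

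| Assumed placebo proportion | Greatest possible power |
|---|---|
| 60% | 0.99 |
| 70% | 0.91 |
| 80% | 0.54 |
| 85% | 0.26 |
| 90% | 0.06 |
| 95% | 0.003 |

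**Step 3: is such a high placebo proportion likely?** Suppose 0.2, 0.3, 0.5 or 1 AE per subject-month, that is means μ of 1.8, 2.7, 4.5 and 9 over nine months. The proportion with at least one AE is:

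- Poisson, 1 − exp(−μ): 84%, 93%, 99%, above 99.9%.
- Negative binomial, 1 − (1 + aμ)^(−1/a), with a = 0.5: 72%, 82%, 91%, 97%.
- Negative binomial with a = 1: 64%, 73%, 82%, 90%.

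A ceiling is plausible but depends on both the rate and the spread between subjects.

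**Step 4: AE count.** Let background be m0 AEs per subject, rituximab add one, and dispersion k be 0.5. The approximate variance of the log rate ratio is [(1/m0 + k) + (1/(m0 + 1) + k)]/29. For m0 = 2 this is (1.000 + 0.833)/29 = 0.0632, with standard error 0.251. Then ln(1.5)/0.251 − 1.96 = −0.35, so power is 0.36. Over m0 = 0.5, 1, 2, 4 and 8, power is 0.87, 0.66, 0.36, 0.17 and 0.08. There is no ceiling, but the same absolute excess is progressively diluted.

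**Step 5: pre-treatment events.** If 14 days (0.46 month) before treatment were counted at the background rate, a true ratio of 1.50 would become (1.5 × 9 + 0.46)/(9 + 0.46) = 1.48. The effect is small.

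**Step 6: what a grade 3 or higher comparison could show.** Fisher power is 0.22 for 5% versus 20%, 0.35 for 10% versus 30%, and 0.68 for 10% versus 40%. For 80% power the rituximab proportion would need to be 36.5% against 5%, 45% against 10%, or 59% against 20%. If both arms were truly at 10%, the large-sample 95% half-width for the difference is 1.96 × √(2 × 0.10 × 0.90/29) = 0.154. Even a result with no difference would thus leave an excess of about 15 points unexcluded.

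**The case against.** A reader might go further than the documents allow in four ways.

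- **That the analysis counts events from screening onward.** Appendix A is a collection schedule and Section 2.9.2 sets no window. Section 5.4.4 limits AEs to participants who received study drug, and Section 2.6 records baseline symptoms so that later effects can be recognised. Randomization is on the day of first treatment (Section 2.4), so earlier events are balanced in expectation, and Step 5 shows that they matter little. What stands is that the window is undefined.
- **That the comparison is bound to saturate.** Without an IPF rate this cannot be shown. At 60% to 70% on placebo there is ample room, and the count model has no ceiling. Section 5.4.6 can also be read as restricting the AE form to clinically important events that are unexpected or study-related, which would lower the rate; Section 5.4.3.3 has all untoward occurrences recorded.
- **That severe harm is never compared.** The study-wide stopping rule in Section 5.4.3 compares serious event rates between arms, and Section 2.9.2 models hospitalizations and acute exacerbations. These are proxies only. The rule has no stated statistic or threshold, Section 5.4.6 limits serious events to those thought study-related, seriousness is not grade, and hospitalization is only one of the grade 3 descriptors.
- **That a formal hypothesis goes untested.** The sentence in Section 2.10.2 is an expectation under anticipated results. The formal wording in Section 1.2 is an acceptable AE profile.

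It is also fair to say that choosing grade 3 or higher as the main comparison, above the all-grade one, would be a preference, given the low power in a 58-subject biomarker trial.

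**Conclusion.** The point holds in a limited form. Section 2.9.2 has no by-grade AE analysis and no stated onset window, although grade is collected, AE rates are a formal endpoint, and the protocol's own expectation concerns high-grade events. The all-grade measures cannot stand in for that analysis.

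How much the any-AE comparison loses is conditional. It becomes nearly uninformative if the placebo proportion is about 85% or more, which is an assumption. The count comparison loses power as background rises, for example to 0.36 at two background AEs per subject, assuming dispersion 0.5 and one extra AE on rituximab. No bias between arms is shown. Nor would the added analysis settle the Section 2.10.2 expectation; it would give an estimate and show how imprecise it is.

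**What to change.** In Section 2.9.2:

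1. Add a between-arm comparison of grade 3 or higher AEs alongside the all-grade analyses. Give the proportion of subjects, with an exact 95% confidence interval for the difference, and the count per subject, with a 95% interval from an exact method if events are sparse.
2. Limit the AE models to events with onset or worsening after the start of the first infusion and through Month 9, with screening and baseline symptoms as the reference for worsening. This agrees with Section 5.4.4.
3. State that the grade 3 or higher result is an estimate, and that a non-significant difference is not evidence for the expectation in Section 2.10.2.
4. Reconcile the recording statements in Sections 5.4.3.3 and 5.4.6, so that the set of events analysed is known.

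The cost is mainly wording, because grades are already collected. The documents do not include the AE form or say that onset date is a field, so this must be confirmed first; if it is not captured, the form needs that addition. The price is few events and a wide interval, which should be reported as it is.

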1.2 SPECIFIC AIMS

Hypothesis: Our central hypothesis is that antibody-mediated autoimmunity plays an important role in IPF progression. A corollary of this hypothesis is that treatments that reduce autoantibodies in these patients will have a favorable effect on the natural history of this disease. The studies proposed here are primarily designed to determine the magnitude and duration of autoantibody reductions affected by rituximab, as a prelude to design of a definitive Phase III efficacy study. Nonetheless, we hope that experimental treatments may result in clinically-relevant beneficial effects as determined by secondary endpoints: preservation of forced vital capacities or reductions of acute exacerbation incidences.

Specific Aims:

1. To conduct a proof-of-concept, mechanistically-driven trial to reduce autoantibodies against epithelial HEp-2 cells among IPF patients.

We hypothesize the experimental treatment with rituximab will more effectively reduce anti-HEp-2 autoantibodies, the primary endpoint of this clinical trial, compared to placebo treatment.

To determine the effects of the experimental rituximab treatment on secondary endpoints of anti-HSP70 autoantibodies, preservation of forced vital capacities, survival, need for hospitalizations, incidences of acute IPF exacerbations, and adverse event-rates.

We hypothesize the experimental treatment will also have a demonstrable effect on these secondary endpoints, in comparison to placebo therapy, and will have acceptable adverse event profile.

Findings of this study will also further develop the potential of focused immunologic assays as prognostic and disease phenotyping tools of individual IPF patients. We anticipate this proposal will establish the feasibility of autoantibody-targeted interventions, and results here will be a nidus for subsequent incremental clinical trials in this population.

The preliminary data that support our central hypothesis are novel findings from a series of innovative investigations.

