2.8.2. Secondary End-Points

Secondary end-points are: a.) treatment-related effects on anti-HSP70 concentrations, b.) forced vital capacities, c.) incidences of acute IPF exacerbations, d.) survival durations, e.) hospitalization rates, and f.) adverse event-rates.

- a.) Anti-HSP70 IgG concentrations- We have found anti-HSP70 is ONE OF MANY autoantibodies present in IPF patients, and it happens too to be ONE OF SEVERAL associated with IPF progression (14). Thus, we will be able to test for effects of rituximab on both global autoantibody production (Primary Endpoint), as well as its effects on a particular, clinically-associated specific autoantibody (anti-HSP70), pretreatment and 1,3,6 and 9 months post-treatment. Anti-HSP70 IgG will be measured by ELISA, as detailed in citation #14.
- **b.)** Forced vital capacities (FVC) by spirometry- In addition to FVC, other pulmonary function variables that are not formal endpoints (FEV $_1$, DL $_{CO}$, and O $_2$ requirement at rest and with walking), 6 minute walk distance, and Borg Dyspnea Assessments will be routinely measured pretreatment and at 1,3,6, and 9 months thereafter. These tests are standard operating procedures (SOP) for care of IPF patients at our centers.
- **c.)** Acute exacerbation frequencies- IPF patients typically experience slowly progressive, if somewhat episodic, lung function deterioration. Nonetheless, a sizeable proportion, variously estimated as 10-to-50% or more, develop acute exacerbations that can result in very rapid onset respiratory failure and death within days (4). Results of studies indicate that autoantibodies are involved in acute exacerbations of IPF. It is hoped that rituximab therapy will decrease the frequency or delay onset of acute exacerbations. Acute exacerbations will be defined by

participating physicians using current consensus criteria, i.e., worsening hypoxemia and dyspnea within the preceding 30 days, characteristic new radiographic pulmonary infiltrates, and no other evident cause of lung dysfunction after thorough clinical assessments (4).

- **d.)** Survival- Given the high mortality of IPF patients, efficacy of the experimental therapy could result in prolonged survival among treated subjects. Survival durations from study enrollment will be tabulated as both absolute survival and transplant-free survival.

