5.4.3.3 Participating Institutions

Each Participating Institution will provide to the Coordinating Center a list of the key personnel assigned to the role for oversight of data management at their site. The general responsibilities for each Participating Institution are as follows:

Commit to accrual to the multi-center protocol.

Submit protocol and/or amendments to their local IRB.

Maintain a regulatory binder.

Update Coordinating Center with research staff changes on a timely basis.

Submit source documents, research records, and CRFs per protocol specific submission guidelines to the Coordinating Center.

Submit Serious Adverse Event reports to local IRB and provide copies to the Coordinating Center

Submit deviations and violations to local IRB and the Coordinating Center.

Assuring patient safety is an essential component of this protocol. The study Principal Investigator has primary responsibility for the oversight of the data and safety monitoring. The study investigators will evaluate all adverse events. All subjects who have AEs, whether considered associated with the use of the study medication or not, must be monitored to determine the outcome. The clinical course of the AE will be followed up according to accepted standards of medical practice, even after the end of the period of observation, until a satisfactory explanation is found or the Principal Investigator considers it medically justifiable to terminate follow-up.

All untoward medical occurrences observed in subjects receiving the study drug will be recorded on the participants' adverse event case report forms (CRF) by the study coordinator under the supervision of the principal investigator. The CRFs will then be reviewed for completeness and internal consistency. Subsequently, the CRFs will be recorded on an electronic password-guarded study database. In addition to internal safeguards built into a computerized system, external safeguards will be put in place to ensure that access to the computerized system and to the data is restricted to authorized personnel. Training conducted by qualified individuals on a continuing basis will be provided to individuals in the specific operations with regard to computerized systems that they are to perform during the course of the study.

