5.4.4 Parameters to be Monitored

The following progress will be monitored throughout the course of the research to ensure the safety of subjects as well as the integrity and confidentiality of their data.

An evaluation of the progress of the research study, including subject recruitment and retention, and an assessment of the timeliness and quality of the data.

A review of collected data (including adverse events, unanticipated problems, and subject withdrawals) to determine whether there is a change to the anticipated benefit-to-risk assessment of study participation and whether the study should continue as originally designed, should be changed, or should be terminated.

An assessment of external factors or relevant information (eg. pertinent scientific literature reports or therapeutic development, results of related studies) that may have an impact on the safety and study participants or the ethics of the research study.

A review of study procedures designed to protect the privacy of the research subjects and the confidentiality of their research data.

The National Cancer Institute Common Toxicity Criteria Scale will be used to define grades (severity) of adverse events and toxicities. An adverse event is any untoward medical occurrence in a participant who received study drug, regardless of its relationship to the study drug. Toxicity is an adverse event with a direct relationship to the study drug. All toxicities are adverse events, but not all adverse events are toxicities. This is a determination made by the study investigator. The study investigators will classify adverse events as "definitely or most likely," "possibly," or "very unlikely" due to the study drug. Toxicity will be defined as an adverse event that is definitely, most likely, or possibly caused by the study drug.

The severity of adverse changes in physical signs or symptoms will be classified as follows:

Grade 1 (Mild): asymptomatic or mild symptoms; clinical or diagnostic observation only; intervention not indicated.

Grade 2 (Moderate): minimal, local or noninvasive intervention indicated; limiting age-appropriate instrumental ADL (Activities of Daily Living).

Grade 3 (Severe): medically significant but not immediately life-threatening; hospitalization or prolongation of hospitalization indicated; disabling; limiting self care ADL.

Grade 4 (Life-threatening): serious potential consequences; urgent intervention indicated.

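### The final analysis compares only all-cause adverse events by arm, which is insensitive to drug harm; toxicities, grade 3 or higher events and SAEs have no final comparison

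*Combined protocol and SAP*

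**What the plan says.** Adverse event rates are secondary endpoint (f) in section 2.8.2, and section 1.2 hypothesizes that rituximab will affect the secondary endpoints "in comparison to placebo therapy, and will have acceptable adverse event profile". The by-arm analyses are in section 2.9.2: "Both the proportion of individuals with AEs and the count of AEs per person will be compared by treatment". The proportion is analysed by logistic regression and the count by a negative binomial model. The same section gives acute exacerbations and hospitalizations their own logistic comparisons. Its exploratory paragraph names mixed-effects and survival models, but not AE grade or relatedness.

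The definition is broad: "An AE is defined as any untoward medical occurrence in a subject, regardless of its relationship to these treatments". Section 5.4.4 separates out a narrower class, "Toxicity will be defined as an adverse event that is definitely, most likely, or possibly caused by the study drug", and sets out severity grades 1 to 5. Section 2.10.2 makes a prediction about severity: "we do not believe high grade AE will be significantly more frequent among experimental trial subjects compared to placebo".

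Two sentences govern what goes on the AE form. Section 5.4.3.3 is inclusive: "All untoward medical occurrences observed in subjects receiving the study drug will be recorded". Section 5.4.6 is narrower and speaks of clinically important events that are either unexpected or study-related.

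The stopping rule at the end of section 5.4.3.3 compares SAE rates between arms. Section 5.4.6 limits SAEs to events the investigator thinks are study-related.

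**The concern.** The trial is meant to say whether rituximab has an acceptable safety profile in IPF and to inform a Phase III design. Any AE and total AE count measure overall burden, which is a legitimate quantity. They are weak evidence on what the drug does, because in a sick population followed by visits and calls for nine months most subjects may have some AE whichever arm they are in. A finding of no difference could then be read as safety when the measure had little chance of showing harm.

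The protocol already has sharper classes in toxicity and grade, and makes a by-arm prediction about high-grade events. No committed final analysis uses the classes or checks the prediction.

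There is a secondary, conditional issue. Acute exacerbations meet the AE definition, and the protocol says of them: "It is hoped that rituximab therapy will decrease the frequency or delay onset of acute exacerbations". If that hope were met and exacerbations were entered as AEs, the same total would carry a drug benefit and a drug harm with opposite signs.

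**Working it through.** **Inputs from the documents.** 29 per arm and two-sided 0.05 (section 2.9.1); exacerbations "variously estimated as 10-to-50% or more, develop acute exacerbations", with no time window given (section 2.8.2); reaction rates in rheumatoid arthritis patients of 8%, 8%, 7% and 6% on rituximab v 5%, 5%, 6% and 4% on placebo (section 3.4).

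**Assumptions.** The documents give no IPF rates for toxicity, high-grade or background AEs. I assume independent events, background AE risk b = 50% to 90% in both arms, exacerbation risk e = 10% to 50%, and drug-type harm c of 2% on placebo and 10%, 20% or 30% on rituximab. Fisher's exact test stands in for the logistic model.

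**Step 1: the plan's own figure.** Exact power of the two-sided Fisher test at 33% v 3%, 29 per arm, is 0.810, which agrees with the stated 80%. The AE comparisons have no stated power.

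**Step 2: harm compared directly.** The same calculation gives 3.8% at 10% v 2%, 37.8% at 20% v 2% and 78.2% at 30% v 2%.

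**Step 3: the same 30% v 2% harm seen through any AE, exacerbations unchanged.** P(any AE) = 1 − (1 − b)(1 − e)(1 − c). For b = 50%, e = 10%: placebo 1 − 0.5 × 0.9 × 0.98 = 55.9%; rituximab 1 − 0.5 × 0.9 × 0.7 = 68.5%.

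| b | e, both arms | Placebo | Rituximab | Difference (points) | Power |
|---|---|---|---|---|---|
| 50% | 10% | 55.9% | 68.5% | +12.6 | 10.2% |
| 50% | 30% | 65.7% | 75.5% | +9.8 | 7.8% |
| 70% | 30% | 79.4% | 85.3% | +5.9 | 4.1% |
| 90% | 50% | 95.1% | 96.5% | +1.4 | 0.1% |

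A true 28-point harm appears as 1 to 13 points. If exacerbations are never entered as AEs (e = 0), the figures are 51.0% v 65.0% with power 12.0% at b = 50%, and 90.2% v 93.0% with power 1.0% at b = 90%. The dilution therefore does not depend on how exacerbations are recorded.

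**Step 4: AE count.** Simulation of the negative binomial comparison used 29 per arm, other AEs with an assumed mean of 2 per person and dispersion 0.5, harm 30% v 2%, and 3,000 runs per case. It rejects in the harm direction in roughly 8% of runs with no exacerbation effect, 5% to 6% if exacerbations fall from 30% to 15%, and 3% if they fall from 50% to 25%. Most of the loss from 78% is already there with no exacerbation effect.

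**Step 5: the conditional offset.** Suppose rituximab halves exacerbations from 30% to 15%, they are entered as AEs, and harm is 10% v 2%. At b = 50%: rituximab 1 − 0.5 × 0.85 × 0.90 = 61.75%; placebo 1 − 0.5 × 0.70 × 0.98 = 65.7%; difference −4.0 points. It is −2.4 at b = 70% and −0.8 at b = 90%. With exacerbations unchanged at b = 50% it is +2.8, the right sign. For harm of 30% v 2% at b = 50%, the +9.8 of step 3 becomes +4.55 with halving from 30% (70.25% − 65.7%), and −1.75 with halving from 50% (73.75% − 75.5%).

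The protocol's own arthritis rates show the same for counts. The excess is (0.08 + 0.08 + 0.07 + 0.06) − (0.05 + 0.05 + 0.06 + 0.04) = 0.29 − 0.20 = 0.09 per person. Halving exacerbations, one event per affected patient, removes 0.05, 0.15 or 0.25 at placebo risks of 10%, 30% or 50%. The net is +0.04, −0.06 or −0.16, and zero at a placebo risk of 2 × 0.09 = 18%.

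**The case against.** A reader might infer that benefit and harm will cancel in the planned AE analyses, so that the AE result will point the wrong way. The documents do not support this as a general statement:

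- The cancellation needs rituximab to prevent exacerbations. Section 2.10.2 treats that expectation as much more speculative than the antibody effects, and the halving used above is an assumption.
- It needs exacerbations to be entered as AEs. Section 5.4.3.3 implies that they are. Under the narrower sentence in section 5.4.6, an expected exacerbation judged unrelated might not be.
- The reversals are small. With both arms given intravenous methylprednisolone and AEs assessed at every contact, background risk may be well above 50%, and −4.0 points at b = 50% is −0.8 at b = 90%. Even −4.0 lies well within one standard error at this size: √[(0.6175 × 0.3825 + 0.657 × 0.343)/29] = 12.6 points.
- Exacerbations are compared separately, so a fall in them would be visible.

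These points stand, and they make the offset a secondary, conditional matter.

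It would also be too strong to say that drug-related harm is never compared by arm. SAEs, defined as study-related, are compared for the stopping rule, and hospitalization, which is part of the grade 3 definition, has its own comparison. But the SAE comparison has no stated test or threshold and belongs to monitoring, and non-serious toxicity falls outside it. Hospitalization is only one route to grade 3. The protocol does keep AE and toxicity apart in its definitions, so the all-cause analysis is not mislabelled. The gap is that nothing sits beside it.

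**Conclusion.** The point holds as a gap in the safety analysis of one secondary endpoint. The committed final AE comparisons are all-cause, and background events dilute drug harm in them: about 78% power for 30% v 2% compared directly, against about 0.1% to 10% through any AE (up to 12% if exacerbations are not counted). These figures rest on assumed harm and background rates, on independence, and on a harm class that captures the drug effect cleanly. Investigator attribution will not be perfect, so 78% is a best case. Masking or reversal by fewer exacerbations is possible only under the conditions above and is not the main reason to act.

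The fix does not make modest harm detectable. At 10% v 2% even the direct comparison has 3.8% power. What it gives is an estimate with an interval that addresses drug harm, and a planned analysis for the high-grade prediction. The primary analysis, sample size and stopping rule are not affected. It is worth doing because it is cheap.

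**What to change.** Add to section 2.9.2 by-arm proportions, with risk differences and exact 95% confidence intervals, for:

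1. toxicities as defined in section 5.4.4;
2. AEs of grade 3 or higher;
3. SAEs.

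Show the all-AE proportion and count with and without events recorded as acute exacerbation. Fix the assignment of events to classes before unblinding. State which of the recording sentences in sections 5.4.3.3 and 5.4.6 governs the AE form, so that both totals are well defined. Keep the all-AE comparisons, labelled as total burden. A by-arm table of worst blood-count grades from the planned CBCs is an optional extra, since cytopenias are listed among the common rituximab risks in section 5.1.2.

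The cost is SAP wording and a few tables; the protocol already provides for grade, attribution, exacerbations and blood counts. The downsides are a few more unadjusted, low-powered secondary comparisons, reliance on investigator attribution for toxicity, and the chance that a drug-related infection misread as an exacerbation drops out of the total without exacerbations. That last risk is why the full total should stay alongside.
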